2.1. Study Design

This is a Phase 1, open label, multi-center, multiple dose, safety, PK, PD and immunogenicity study evaluating the components of VBIR-2 (PF-06936308) in patients with advanced NSCLC and metastatic TNBC. VBIR-2 consists of the following components: AdC68, pDNA, tremelimumab and anti-PD-1 (PF-06801591).

The study is divided into two parts, dose escalation (Part 1) followed by dose expansion (Part 2). The Part 2 dose expansion protocol specifics will be covered in a subsequent amendment once recommended phase 2 dose (RP2D)/MTD is reached in Part 1. The dose escalation (Part 1) is anticipated to have 7 cohorts and estimated to enroll approximately 36 patients in Part 1. The actual number of patients enrolled will depend on the tolerability of the components of the VBIR-2.

[figure not shown]
Part 1 (dose escalation) will include patients with advanced NSCLC and mTNBC for whom no standard therapy is available. Length of treatment is estimated to be 8-22 months, depending on each patient's disease status.

The proposed doses, schedule(s), and PK time points may be reconsidered and amended during the study based on the emerging safety and PK data. The dose level to be carried forward in subsequent cohorts may be different than those depicted in Table 2. If the highest tested dose of one component is not tolerable, then a lower or intermediate dose could be

carried forward in subsequent cohorts. If a component is not tolerable, it could be excluded from the dose escalation.

The overall design is presented in Figure 1.

Figure 1. Overall Study Design Part 1

Maintenance Treatment Schedule for anti-PD-1 (PF-06801591) starting at Month 9, will continue to be administered every 4 weeks.

Maintenance Treatment Schedule for pDNA and tremelimumab after Month 8 will be administered every 8 weeks starting with Month 10.

Treatment will be continued until disease progression, unacceptable toxicity, death, or patient's or investigator's decision.

Part 2 (dose expansion) will require a protocol amendment; only a high level study design is described below. Details of the patient population, inclusion-exclusion criteria, and detailed

study design with statistical calculations will be covered in a subsequent amendment once RP2D/MTD is reached in Part 1.

Part 2 will enroll patients in a design with 3 simultaneous non-randomized cohorts to further evaluate the safety and antitumor activity of the VBIR-2 regimen in patients with advanced NSCLC and mTNBC.

- *mNSCLC expansion cohorts \geq second line (2L) patients with no more than 2 prior chemotherapy containing regimens:*
 - *Cohort 1 mNSCLC (n ~ 15);*
 - \geq Second line (2L) PD-L1 negative patients (PD-L1 positive < 1%).
 - *Cohort 2: mNSCLC (n ~ 20);*
 - \geq 2L patients who are PD-L1 positive \geq 1% with approximately equal number of patients who have low and high PD-L1 expression (1%-49% and \geq 50% respectively).^{2, 3}
- *mTNBC expansion cohort \geq 2L mTNBC patients (all subtypes) with no more than 2 prior chemotherapy containing regimens:*
 - *Cohort 3: mTNBC (n ~26);*
 - \geq 2L mTNBC (all subtypes).

Patients will participate in the treatment period of the study for approximately 9-12 months depending on type of advanced disease. This includes a 28 day screening period followed by two cycles of treatment (each 4 months in duration for a total of 8 months). After completion of two cycles, patients will then enter the maintenance phase of the study.

Treatment will continue until: disease progression, unacceptable toxicity, death or patient's or investigator's decision occurs. Patients who demonstrate clinical benefit with manageable toxicity and who are willing to continue receiving study treatment will be given the opportunity to continue treatment upon agreement between the investigator and sponsor. When the patient discontinues treatment, they will then enter a 6 month post-dose follow-up period to assess safety and pharmacodynamics. The end of the study is the last patient last visit.

The treatment effect of cancer immunotherapy can often be delayed. Therefore, patients should be encouraged to continue on study treatment for at least 24 weeks before an investigator considers removing the patient due to disease progression, as long as:

- *Patient and investigator agree.*
- *Patient continues to meet all other study protocol eligibility criteria.*
- *Acceptable toxicity.*
- *No deterioration of patient performance status.*

2.1.1. Starting Dose Part 1

The dose escalation could include an increase in the dose of one component of the regimen or could include the addition of the lowest dose of an additional component. Seven planned dose escalation cohorts may be investigated:

- $(AdC68 2 \times 10^{11} VP + 5 \text{ mg pDNA})$.
- $(AdC68 6 \times 10^{11} VP + 5 \text{ mg pDNA})$.
 - If needed – dose reduction of the $AdC68$ dose to $2 \times 10^{11} VP$ is allowed.
- $(AdC68 6 \times 10^{11} VP + 5 \text{ mg pDNA} + 40 \text{ mg tremelimumab})$.
- $(AdC68 6 \times 10^{11} VP + 5 \text{ mg pDNA} + 40 \text{ mg tremelimumab} + 130 \text{ mg PF-06801591})$.
 - If needed – dose reduction of the tremelimumab dose is allowed.
- $(AdC68 6 \times 10^{11} VP + 5 \text{ mg pDNA} + 40 \text{ mg tremelimumab} + 300 \text{ mg PF-06801591}^*)$.
- $(AdC68 6 \times 10^{11} VP + 5 \text{ mg pDNA} + 80 \text{ mg tremelimumab} + 300 \text{ mg PF-06801591}^*)$.
- $(AdC68 6 \times 10^{11} VP + 5 \text{ mg pDNA} + 150 \text{ mg tremelimumab} + 300 \text{ mg PF-06801591}^*)$.

Note: *If needed, dose reduction of the tremelimumab dose is allowed in cohorts with 300 mg anti-PD-1 (PF-06801591) (see Section 5.4.3.2 in the protocol).

2.1.2. Criteria for Dose Escalation

The principles of modified toxicity probability interval (mTPI) design (Ji et al., 2010)4, will be utilized for the dose escalation portion of the study.

An mTPI design, targeting a DLT rate of 27.5% and an acceptable DLT equivalence interval (22.5% to 32.5%), will be utilized in the dose escalation phase.

The dose levels to be evaluated are given in Section 2.1.1 in the protocol. If a high DLT rate is observed at the starting dose, the study may explore a lower dose or may be stopped.

Each cohort would enroll 2 to 4 DLT evaluable patients and at least 6 and up to 12 patients would be enrolled at a dose level that is predicted to be the MTD as per the mTPI method. Dose cohorts with an acceptable safety profile may be expanded up to $N=12$ to further assess safety, CCI [REDACTED] pharmacokinetics, CCI [REDACTED]. Decisions to enroll additional patients at dose levels already cleared for safety will be based on clinical judgment.

The mTPI method relies upon a statistical probability algorithm, calculated using all patients treated in the current dose level to determine one of the following dose-finding decisions: the subsequent dose should be escalated, maintained at the current dose, or de-escalated in the next cohort of 2 to 4 patients, or the trial should be terminated. It is currently envisaged that $AdC68 6 \times 10^{11} VP + 5 \text{ mg pDNA} + 150 \text{ mg tremelimumab} + 300 \text{ mg ANTI-PD-1 (PF-06801591)}$ will be RP2D.

Decision rules are based on calculating posterior probabilities of 3 dosing intervals corresponding to under, proper, and over dosing in terms of toxicity. Specifically, the underdosing interval is defined as $(0; pT-e1)$, the over-dosing interval $(pT+e2, 1)$, and the proper-dosing interval $(pT- e1, pT+ e2)$, where $e1$ and $e2$ are small fractions. In study, $e1$ is

selected as 0.05 and e_2 is selected as 0.05, therefore, the target interval for the DLT rate is (0.225, 0.325). The 27.5% target, the symmetry of the Equivalence Interval and its upper limit were chosen based on safety considerations. The prior distribution of DLT is set as a beta (0.5, 0.5), and the threshold probability for early termination and dose exclusion is set to 0.95. Even though the upper limit of the mTPI is higher than 27.5%, doses with an incidence of DLT > 27.5% (eg, 3 out of 9) cannot be declared as the MTD.

The 3 dosing intervals are associated with 3 different dose-escalation decisions. The underdosing interval corresponds to a dose-escalation I, overdosing corresponds to a dose de-escalation (D/U), and proper dosing corresponds to remaining at the current dose (S).

Table 1. Decision Rules

#DLTs	1	2	3	4	5	6	7	8	9	10	11	12
0	E	E	E	E	E	E	E	E	E	E	E	E
1	D	S	S	S	E	E	E	E	E	E	E	E
2		U	D	S	S	S	S	S	S	E	E	E
3			U	U	D	D	S	S	S	S	S	S
4				U	U	U	U	D	S	S	S	S
5					U	U	U	U	U	D	S	S
6						U	U	U	U	U	U	U

- Columns indicate number of patients in the cohort and rows indicate number of patients with DLTs
E= Escalate to the next higher dose; S: Stay at the same dose; D: De-escalate to the previous lower dose; U: De-escalate to the previous lower dose and the current dose will never be used again in the trial

If a patient discontinues close to Day 28 for reasons other than toxicity and due to an evident non drug-related event, the patient may be deemed evaluable for safety if safety assessments have been unremarkable and the investigator and sponsor's medical monitor both agree that the patient is evaluable for DLT safety observation.

The dose escalation Part 1 of the study will stop if any of the following criteria is met:

1. The maximum sample size has been achieved (approximately 36 patients in total as per the current dosing schedule);
2. 6 to 12 patients have been enrolled at a dose level that is predicted to be the MTD according to Table 1;
3. All dose levels explored appear to be overly toxic, and the MTD cannot be determined;
4. All candidate dose levels have been tested and deemed safe.

As an example, if the total number of patients (cumulative in the study) treated at the current dose is 4, the following dosing rules are applied:

- 0 DLT -> escalate
- 1 DLT -> remain at the same dose
- 2 DLTs -> De-escalate to the previous or intermediate lower dose
- 3-4 DLTs -> De-escalate and consider current dose as intolerable

Activation of each cohort will occur no sooner than 28 days after the first 2-4 patients receive the first AdC68 vaccination, but may occur later if the sponsor and investigators determine additional safety data is needed. The Pfizer clinical team and investigators will review all available safety data from the previous and current cohorts prior to making a decision to dose escalate. If no safety issues that would prohibit dose escalating are observed, the next cohort of patients would be open for accrual.

If dose escalation continues up to a predefined Maximum Feasible Dose (MFD), the escalation is halted without a maximum tolerated dose (MTD) estimate. In those circumstances, the MFD may be the recommended Phase 2 dose (RP2D).

2.1.3. DLT Definition

Severity of adverse events (AEs) will be graded according to the details specified in the protocol.

2.1.4. MTD Definition

The MTD is defined as the highest dose with true toxicity probabilities in the equivalence interval (EI) where the EI is defined as (22.5%, 32.5%).

Even though the mTPI model may select an MTD with an incidence of DLTs that is higher than 32.5% since mTPI decision rules are based on unit probability mass (UPM) and not on point estimates of the DLT rate (see Section 9.2.1), doses with an incidence of DLT >32.5% (eg, 3 out of 9) cannot be declared as the MTD. In practice, model recommendations may be overridden by clinical judgment, and MTD with an incidence of DLTs that is higher than 32.5% will not be considered acceptable to be selected as MTD.

2.1.5. Late Onset Toxicity and Toxicities Observed in the Expansion Phase

Adverse events that meet the same grading criteria as the DLT criteria listed above occurring after the DLT observation period in Part 1, but before completion of the first cycle of treatment will lead Pfizer to immediately schedule a meeting with the investigators to review the details of the potential late onset toxicity and determine if the enrollment has to be held for this dose level, continued, or if a dose reduction should be implemented for all ongoing patients. Late onset toxicities meeting the definition of a DLT will be used in the evaluation of the MTD.

In addition, adverse events that meet the same grading criteria as the DLT criteria listed above will prompt Pfizer to immediately schedule a meeting with the investigators to review

the details of the toxicity and determine the necessary action to be implemented for all patients.

2.1.6. Recommended Phase 2 Dose (RP2D) Definition

The RP2D is the dose chosen for further investigation based on Phase 1 study results. If the MTD proves to be clinically feasible for long-term administration in a reasonable number of patients, then this dose usually becomes the RP2D. Further experience with the MTD may result in a RP2D dose lower than the MTD.

2.2. Study Objectives

Primary Objectives:

- *To assess safety and tolerability of increasing dose levels of VBIR-2.*
- *To characterize the dose limiting toxicities (DLTs) and overall safety profile of escalated doses of VBIR-2.*
- *To assess safety and tolerability at increasing dose levels of VBIR-2 components in successive cohorts of patients in order to estimate the Maximum Tolerated Dose (MTD) and select the Recommended Phase 2 Dose (RP2D)/schedule.*

[figure not shown]
Secondary Objectives:

- *To evaluate the immune response elicited by VBIR-2 to the 3 selected tumor antigens.*
- *To evaluate the PK of tremelimumab and of anti-PD-1 (PF-06801591) after SC administration.*
- *To evaluate the anti-drug antibody (ADA) response of tremelimumab and anti-PD-1 (PF-06801591) after SC administration with the other components.*

 C

- *To document any preliminary evidence of anti-tumor activity.*

CC1

3. INTERIM ANALYSES, FINAL ANALYSES AND UNBLINDING

There are no formal interim statistical analyses in this open-label, unblinded clinical trial. Treatment safety and effectiveness are to be monitored continuously.

A check for futility will be carried out after at least 10 patients are enrolled in each cohort in Part 2 as detailed in Section 4.

4. HYPOTHESES AND DECISION RULES

4.1. Statistical Hypotheses

The expansion phase of the study (Part 2) will consist of three single arm cohorts: Cohort 1B, 2B and 3B respectively; the recommended dose from Part 1 will be used in this phase. Approximately n=15 patients would be enrolled in Cohort 1B of mNSCLC \geq 2L PD-L1 negative patients and n=20 in Cohort 2B, approximately n=10 mNSCLC \geq 2L patients who are PD-L1 positive >1% and <50% and n=10 mNSCLC \geq 2L patients who are PD-L1 positive \geq 50%. For the mTNBC cohort, the study will enroll n=26 patients and have approximately 80% power with 1-sided alpha=0.1 to detect an ORR of 50% with a null hypothesis of 30% ORR.

4.2. Statistical Decision Rules

See [Section 2.1.2](#) for the details of the decision rule of dose escalation part.

5. ANALYSIS SETS

5.1. Full Analysis Set

The full analysis set includes all enrolled patients.

5.2. Pharmacokinetic Analysis Set

[figure not shown]
5.2.1. Concentration Analysis Set

There are two moieties measured from PK perspective; PF-06801591 and tremelimumab. Hence there are two PK concentration analysis sets. For each moiety, the PK concentration population is defined as all enrolled subjects treated who have at least 1 concentration in at least 1 treatment period and who do not have major protocol deviations.

5.2.2. Parameter Analysis Set

There are two moieties measured from PK perspective; PF-06801591 and tremelimumab. Hence there are two PK parameters analysis sets. For each moiety, the PK parameter analysis population is defined as all enrolled subjects treated who have at least 1 of the PK parameters of interest in at least 1 treatment period and who do not have major protocol deviations.

CCI

5.4. Safety Analysis Set

All subjects who receive at least 1 dose of study medication will be included in the safety analyses and listings.

5.5. Other Analysis Sets

- *Per protocol analysis set.*

The per protocol (PP) analysis set includes all enrolled patients who receive at least one dose of all assigned regimen components administered Cycle 1 Day 1 of study medication and who do not have major protocol deviations during the 28 days after the first vaccination.

- *Modified Intention-to-Treat analysis set.*

CCI modified
Intention-to-Treat (mITT), which is defined as all enrolled patients who received at least one dose of all assigned regimen components administered. CCI

CCI a patient must have at least 1 valid and determinate assay result related to the proposed analysis. Patients who have no valid and determinate assay result related to any proposed analysis will be excluded from the mITT analysis set.

CCI

- *Immunogenicity analysis set.*

The immunogenicity analysis set includes all enrolled patients who receive at least one dose of the VBIR-2 component that is the subject of the immunogenicity assessment (tremelimumab or anti-PD-1 (PF-06801591)).

5.6. Protocol Deviations

Subjects who experience events that may affect their PK profile (eg vomiting) may be excluded from the PK analysis. At the discretion of the pharmacokineticist a concentration value may also be excluded if the deviation in sampling time is of sufficient concern or if the concentration is anomalous for any other reason.

A full list of protocol deviations will be compiled and reviewed to identify major and minor deviations prior to database closure.

5.6.1. Deviations Assessed Prior to Randomization

At screening, the investigator will assess subjects against the inclusion and exclusion criteria as set out in Sections 4.1 and 4.2 of the protocol.

5.6.2. Deviations Assessed Post-Randomization

Any significant deviation from the protocol will be reviewed prior to database closure and a decision taken regarding evaluation for each analysis population.

6. ENDPOINTS AND COVARIATES

6.1. Efficacy Endpoint(s)

CCI

The main

analysis populations will be based on mITT and EP (see Section Analysis Sets).

Disease response will be presented in the form of patient data listings that include, but are not limited to starting dose, disease response at each visit, and best overall response. In addition, progression date, death date, date of first response and last disease assessment date, and date of last contact will be listed.

Summary of objective response rates will be provided by descriptive statistics. Objective tumor response, as assessed using the Response Evaluation Criteria in Solid Tumor (RECIST) version 1.1 by calculating the Objective Response Rate (ORR) and Progression-Free Survival (PFS).

Progression-free survival (PFS) is the time from start date to date of first documentation of progression, or death due to any cause. Progression is defined as the appearance of local, regional or distant disease of the same type after complete response or progression of pre-existing lesions. It does not include second primary malignancies of unrelated types.

Overall survival (OS) is the time from start date to date of death due to any cause.

Duration of Response (DOR) is defined as the duration of overall response measured from the time measurement criteria are met for complete response (CR) or partial response (PR) (whichever is first recorded) until the first date that recurrent or progressive disease is objectively documented (taking as reference for progressive disease the smallest measurements recorded since the treatment started).

Duration of Stable Disease (DOSD) is defined as stable disease measured from the start of the treatment until the criteria for progression are met, taking as reference the smallest measurements recorded since the treatment started, including the baseline measurements.

For tumor response data, the following analyses may be performed:

1. Tumor response (CR, PR, SD, PD, etc.) by cohort and visit, separately for RECIST 1.1 and irRECIST. Investigator provided tumor response will be presented by descriptive statistics (frequency and percentage).

2. Best overall response, by cohort, across all available tumor assessments from both treatment period and maintenance period, separately for RECIST 1.1 and irRECIST. Best overall response will be derived programmatically. In the tabular data presentation, a row of CR+PR will be added to show the results of ORR. With RECIST 1.1, tumor response (CR or PR) confirmation is optional as response rate is not the primary endpoint of the study, hence unconfirmed best overall response will be derived and presented. With irRECIST, tumor response (irCR or irPR) and disease progression (irPD) are required to be confirmed, however in this study tumor response confirmation is not required, therefore unconfirmed best overall response will be derived and presented. Descriptive statistics (frequency and percentage) will be provided.

In the “unconfirmed” analyses (ie, tumor response or progression without confirmation required), all tumor assessments data will be included for analyses. Specifically, regardless if a patient’s tumor response or progression is subsequently confirmed or not, the patient data will all be included in the “unconfirmed” analyses. This is a more comprehensive analysis where tumor confirmation is not required and not taken into account. For example in the ORR analysis, if a patient achieved CR or PR, regardless it is subsequently confirmed or not, the patient will be included in the numerator.

Additional summary combining data across different cohorts may be generated if deemed necessary. Swimmer plots will be used to display duration of treatment and tumor response at each applicable time point. Waterfall plot for individual tumor size percent change from baseline, and spider plot for individual tumor size percent change from baseline over time will be presented. These plots will be presented for RECIST 1.1 and irRECIST separately.

For all time-to-event endpoints, the Kaplan-Meier analysis may be performed if deemed necessary at the time of data analysis. If the Kaplan-Meier analysis is performed for progression-free survival, an event is defined as the first occurrence of “PD” status by investigator or death, whichever comes first, under RECIST; and is defined as the first occurrence of “irPD” status that has been subsequently confirmed or death, whichever comes first, under irRECIST. Time zero for all time-to-event analyses will be defined as the first vaccination on Cycle 1 Day 1. **CCI**

Antitumor response and tumor control duration based on total measurable tumor burden as assessed by the Immune-Related Response Criteria Derived from RECIST 1.1 (irRECIST) (Appendix 4).

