		Cycle 1					Cycle 2					End of Treatment ³²	Follow- Up (Months after EOT visit)				Survival Follow-up ³⁴	
Study Day		Day 1	Day 8	Day 15	Day 22	Day 29	Day 43	Day 57	Day 71	Day 85	Day 113						Post 6-Month Follow-up	
Cycle Day											Day 1	Day 29	Day 57	Day 85	Day 99	Every 3 Months		
Visit Window (Days)*		±1	±2	±2	±2	±4	±2	±4	±2	±2	±2	±2	±2	±2	±4	±4	±10	

21. **Registration:** Participant number and dose level allocation operated by Pfizer Inc.

22. **Investigational Product Administration:** Treatment to be administered after all other assessments required on that day have been performed.

23. **Tumor Assessments:** Tumor assessments will include all known or suspected disease sites. Screening images may be obtained within 5 weeks of registration. Imaging obtained as part of standard of care but within 28 days (-7 days) of registration may be used for screening assessment. Imaging may include chest, abdomen and pelvis CT or MRI scans, and bone scans. Bone scans will be performed at baseline if disease is suspected and on study as appropriate to follow disease. Baseline central nervous system (CNS) imaging MRI or CT Brain to be conducted only if clinically indicated based on the investigator's judgement. CT or MRI scans, as well as bone scans, when indicated, are to be done every 8 weeks (±5 days) with the first one to occur 8 weeks after C1D1 Repeat imaging will be completed every 8 weeks up to and including Month 8 (Week 32) or until disease progression that requires new treatment modality, permanent discontinuation, or death. Disease progression will be confirmed with 2 consecutive timepoints at least 4-8 weeks apart in the absence of rapid clinical deterioration. Tumor assessment should be repeated at the End of Treatment visit if more than 6 weeks have passed since the last evaluation.

CCI

25. **Acetylcholine receptor (AChR) antibody:** Sample to be sent to the central laboratory for analysis. CCI

The evaluation for AChR antibodies is included to exclude participants who test positive at screening as agreed upon with the United States Food and Drug Administration (US FDA) and to confirm requirement for evaluation if myasthenia gravis is suspected.⁹⁹

CCI

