2.2. Part 2: Dose Expansion Objectives and Endpoints

Primary Objective(s): Part 2	Primary Endpoint(s): Part 2

 • To document preliminary evidence of anti-tumor activity using the Clinical Benefit rate (CBR) in participants with NSCLC. • To assess safety and tolerability of VBIR-2 in participants with NSCLC. 	
 • CBR (proportion of participants who achieve Complete Response, Partial Response or Stable Disease for > 6 months) using the Response Evaluation Criteria in Solid Tumor (RECIST) version 1.1 (Appendix 3). • Adverse Events as characterized by type, frequency, severity, timing, seriousness, and relationship to study therapy. • Laboratory abnormalities as characterized by type, frequency, severity, and timing.
Secondary Objective(s): 
 • To document preliminary evidence of anti-tumor activity in participants with NSCLC. • To evaluate the PK of tremelimumab and of sasanlimab after SC administration. • To evaluate the anti-drug antibody (ADA) response of tremelimumab and sasanlimab after SC administration with the other components. 	Secondary Endpoint(s): 
 • Objective Response Rate (ORR), Duration of Response (DOR) and Progression-Free Survival (PFS) using RECIST version 1.1 (Appendix 3). • Overall survival (OS). • Tremelimumab and sasanlimab trough concentrations after multiple dosing (C_{trough}) at various time points. • Incidence and titers of ADA and neutralizing antibodies against tremelimumab and against sasanlimab.

CCI

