9.4. Efficacy Analysis

In this First-In-Patient study anti-tumor activity is a secondary CCI objective. The main analysis populations will be based on mITT and EP (see Section [Analysis Sets](#)).

Disease response will be presented in the form of participant data listings that include, but are not limited to starting dose, disease response at each visit, and best overall response. In addition, progression date, death date, date of first response and last disease assessment date, and date of last contact will be listed.

Summary of objective response rates (ORR) and clinical benefit rate (CBR) will be provided by descriptive statistics.

Progression -free survival (PFS) is the time from start date to date of first documentation of progression, or death due to any cause. Progression is defined as the appearance of local, regional or distant disease of the same type after complete response or progression of pre-existing lesions. It does not include second primary malignancies of unrelated types.

Overall survival (OS) is the time from start date to date of death due to any cause.

Duration of Response (DOR) is defined as the duration of overall response measured from the time measurement criteria are met for complete response (CR) or partial response (PR) (whichever is first recorded) until the first date that recurrent or progressive disease is objectively documented (taking as reference for progressive disease the smallest measurements recorded since the treatment started).

Duration of Stable Disease (DOSD) is defined as stable disease measured from the start of the treatment until the criteria for progression are met, taking as reference the smallest measurements recorded since the treatment started, including the baseline measurements.

Clinical Benefit Rate (CBR) is defined as the proportion of participants who achieved anti-tumor responses of Complete Response (CR), Partial Response (PR), or Stable Disease for > 6 months (SD).

The Kaplan--Meier methods will be used to analyze all time to event endpoints. Details of these endpoint analyses methods will be included in the Statistical Analysis Plan.

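### Carrying the SAP's waiver of response confirmation into Part 2 would let single unconfirmed CR/PR scans into the primary clinical benefit rate

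*SAP*

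**What the plan says.** **SAP 6.1 (Efficacy Endpoint(s)).** For RECIST 1.1, "confirmation is optional as response rate is not the primary endpoint of the study, hence unconfirmed best overall response will be derived and presented". For ORR the rule is explicit: "if a patient achieved CR or PR, regardless it is subsequently confirmed or not, the patient will be included in the numerator". Tumor response is the investigator's, and best overall response is taken over all available assessments. SAP Section 2 ties the document to the protocol of 16 March 2018, SAP 6.2.1 names DLT as the primary endpoint, and CBR is not mentioned.

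**Protocol 2.2 (Part 2 objectives and endpoints).** A primary objective is "To document preliminary evidence of anti-tumor activity using the Clinical Benefit rate (CBR) in participants with NSCLC". The matching endpoint is "CBR (proportion of participants who achieve Complete Response, Partial Response or Stable Disease for > 6 months", by RECIST 1.1. Secondary endpoints include "Objective Response Rate (ORR), Duration of Response (DOR) and Progression-Free Survival (PFS) using RECIST version 1.1".

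**Protocol 9.4 (Efficacy Analysis).** CBR is the proportion with "Complete Response (CR), Partial Response (PR), or Stable Disease for > 6 months (SD"; the placing of the label ties the time condition to stable disease. The section opens "In this First-In-Patient study anti-tumor activity is a secondary", and the text that follows is redacted.

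**Protocol 7.4 and Appendix 3.** Response is assessed by RECIST 1.1, status by status at each evaluation. Neither place requires a CR or PR to be confirmed.

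**The concern.** The SAP gives one reason for not confirming responses: response rate is not primary. That was sound for the protocol version it covers. Under Amendment 2, CR and PR are two of the three ways to count as a success on a Part 2 primary endpoint. If the rule is carried over, its reason no longer applies. If it is not carried over, the current protocol has no rule at all.

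A reading near the 30% shrinkage line on one scan would then be enough to score clinical benefit, even with progression at the next scan. The cohort is open-label, has no control arm, holds about 30 participants and is read by the investigator (Protocol 7.4 only keeps images available for possible peer review). A few such readings could noticeably change the primary estimate.

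**Working it through.** **Inputs**

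- Part 2 size: about 30, one cohort (Protocol 9.3).
- Scans: every 8 weeks, ±5 days, to Week 32 (Protocol, Part 2 Schedule of Activities, note 23).
- Month length: 28 days (Protocol, Part 2 maintenance schedule), used here as the most lenient reading of 6 months: 6 × 28 = 168 days.
- Prior and threshold: Jeffreys, Beta(0.5, 0.5), and 20%, both from the example in Protocol 9.3.
- Number of unconfirmed responders without lasting control, *u*: not given in the documents. It is assumed to be 0 to 4 of 30, for illustration only.

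**Step 1. The plan's own figure.** Protocol 9.3 says 14/30 responders give a 77% posterior probability that the rate is not below 20%. The posterior is Beta(14.5, 16.5). P(rate > 20%) = 0.9995, not 0.77; a 40% threshold gives 0.773. So the example does not reproduce. That is a separate error, and the present point does not rest on it.

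**Step 2. Does any text require confirmation of CR/PR?** SAP 6.1 waives it. Protocol 2.2, 7.4, 9.4 and Appendix 3 are silent. The answer is no on either document.

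**Step 3. What the rules do on the scan schedule**

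| Course | CBR, unconfirmed rule | CBR, confirmation rule with unconfirmed treated as SD |
|---|---|---|
| PR Week 8, PD Week 16 (16 × 7 = day 112) | counts | does not count (112 < 168) |
| PR Week 8, PR Week 16, PD Week 24 | counts | counts |
| SD, then PD Week 24 (24 × 7 = day 168) | does not count (168 is not more than 168) | does not count |

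Only the top row changes. Confirmation removes the one-scan response; it does not alter how durable a confirmed response must be.

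**Step 4. Does the existing schedule supply the confirming scan?** With both windows at their extremes, two consecutive 8-week scans are at least 56 − 10 = 46 days apart, which exceeds 28.

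**Step 5. Size per participant.** 1/30 = 3.3 percentage points. It applies to ORR for every unconfirmed responder, and to CBR for those who do not also stay free of progression beyond 6 months.

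**Step 6. Illustration on the plan's Bayesian scale.** With *x* counted benefits and *u* of them removed, the posterior is Beta(*x* − *u* + 0.5, 30 − *x* + *u* + 0.5). Starting from 9/30:

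| *u* (assumed) | CBR | P(CBR > 20%) |
|---|---|---|
| 0 | 30.0% | 0.910 |
| 1 | 26.7% | 0.822 |
| 2 | 23.3% | 0.689 |
| 3 | 20.0% | 0.519 |
| 4 | 16.7% | 0.338 |

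Starting from 14/30, four removals (10/30, 33.3%) move the probability only from 0.9995 to 0.960. The choice of rule therefore matters when the observed rate is near 20% and little when it is far above.

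**The case against.** **The SAP predates the endpoint.** It covers the 2018 protocol, leaves Part 2 detail to a later amendment and never names CBR. This stands: no document says that the unconfirmed rule applies to CBR, so it gets there only by carry-over. But Protocol Section 9 sends detailed methodology to the SAP, and the current protocol has the same gap on its own.

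**Section 2.2 could mean that all three categories must last beyond 6 months.** Taken alone, its wording allows that, and a short-lived PR would then not count in CBR. Section 9.4 makes the SD-only reading much the stronger, and ORR would be affected either way.

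**Part 2 is exploratory.** CBR is summarised descriptively with Bayesian estimation, no success threshold is set, and the 20% is only an example. Short responses would show in the visit listings, in DOR and in the planned swimmer and spider plots. All true, and it limits the consequence. The headline primary rate would still be the unconfirmed one.

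**Tempting stronger readings.** A reader might infer that the plan demands more evidence for failure than for success, because the protocol says "Disease progression will be confirmed with 2 consecutive timepoints at least 4-8 weeks apart". That sentence stands in the imaging notes and in Section 3.1.2 beside the text on continuing treatment. In the analysis, SAP 6.1 takes the first PD for RECIST PFS without confirmation, and Protocol 9.4 uses first documented progression. The asymmetry is not there in the analysis. Nor does error in CBR run only upward: one mistaken PD can end SD before 6 months and lower the rate.

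**Conclusion.** The point holds in a limited form. If the SAP's waiver is carried into Part 2, single unconfirmed CR/PR scans enter a primary endpoint without the reason that justified the waiver, and nothing in the current protocol prevents it. Each such participant without control beyond 6 months is worth 3.3 points of CBR and of ORR at n = 30. The number of them, and so the total effect, cannot be derived from the documents; the illustration rests on assumed counts.

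The conclusion assumes the SD-only reading of the 6-month condition in Protocol 9.4 and that no later SAP text settles the matter. It is not a claim about durability: a PR confirmed at Week 16 with PD at Week 24 counts under either rule, because the protocol's CBR definition sets no duration for CR/PR. Whether the net error in CBR is upward is also not established.

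The visible opening of Protocol 9.4 sits badly with Section 2.2, but the redaction hides what qualifies it, so this calls for reconciliation and is not proof of a contradiction.

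**What to change.** 1. Update the SAP to Amendment 2 and define CBR in it, stating that the 6-month condition applies to SD.
2. For Part 2, count a CR or PR in the main CBR and ORR only if confirmed at an assessment at least 4 weeks later. The next scheduled scan serves.
3. Treat an unconfirmed CR or PR as SD, so that it enters CBR only if the more-than-6-month rule is met.
4. Report unconfirmed CBR and ORR beside the main rates as supportive.
5. Reconcile the visible wording of Protocol 9.4 on the status of anti-tumor activity with Section 2.2.

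The cost is wording and programming; no scans are added to the schedule. The main rates may be slightly lower, and a responder who leaves before the next scan is not counted as confirmed. The supportive rates show how many participants that concerns.
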